16.32 Definitions and Analyses of Secondary Endpoints

- 16.321 A tumor response is defined to be a CR or PR noted as the objective status on 2 consecutive evaluations at least 8 weeks apart. Tumor response will be evaluated. All patients meeting the eligibility criteria who have signed a consent form and have begun treatment will be evaluable for response.
- 16.322 Progression-free survival is defined as the time from registration to the earliest date documentation of disease progression or death. Kaplan-Meier curve will be used to estimate progression-free survival time.
- 16.323 Adverse events: All eligible patients that have initiated treatment will be considered evaluable for assessing adverse event rate(s). The maximum grade for each type of adverse event will be recorded for each patient, and frequency tables will be reviewed to determine patterns. Additionally, the relationship of the adverse event(s) to the study treatment will be taken into consideration.
- 16.324 Observation Phase: Retreatment of patients who have relapsed will be left to the discretion of the treating physician. Statistical analysis of the observational phase data for these patients will be of a descriptive nature.

16.4 Data & Safety Monitoring:

16.41 The study chair(s) and the study statistician will review the study at least twice a year to identify accrual, adverse event, and any endpoint problems that might be developing. The Mayo Clinic Cancer Center (MCCC) Data Safety Monitoring Board (DSMB) is responsible for reviewing accrual and safety data for this trial at least twice a year, based on reports provided by the MCCC Statistical Office.

16.42 Adverse Event Stopping Rules: The stopping rules specified below are based on the knowledge available at study development. We note that the Adverse Event Stopping Rule may be adjusted in the event of either (1) the study re-opening to accrual or (2) at any time during the conduct of the trial and in consideration of newly acquired information regarding the adverse event profile of the treatment(s) under investigation. The study team may choose to suspend accrual because of unexpected adverse event profiles that have not crossed the specified rule below.

Accrual will be temporarily suspended to this study if at any time we observe events considered at least possibly related to study treatment (i.e. an adverse event with attribute specified as “possible”, “probable”, or “definite”) that satisfy the following:

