- If 4 or more patients in the first 15 treated patients or anytime thereafter more than 25% of patients experience a \geq grade 4 or higher adverse event, except for hypertension, diarrhea, and abnormal liver function tests, accrual will be temporarily suspended.

We note that we will review grade 4 and 5 adverse events deemed “unrelated” or “unlikely to be related”, to verify their attribution and to monitor the emergence of a previously unrecognized treatment-related adverse event.

16.5 Results Reporting on ClinicalTrials.gov: At study activation, this study will have been registered within the “ClinicalTrials.gov” website. The primary and secondary endpoints (ie, “Outcome Measures”) along with other required information for this study will be reported on ClinicalTrials.gov. For purposes of timing of the Results Reporting, the initial estimated completion date for the Primary Endpoint of this study is 36 months after the study opens to accrual. The definition of “Primary Endpoint Completion Date” (PECD) for this study is at the time the last patient registered has been followed for at least 12 months overall survival status.

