Appendix VII

Table 14 Adverse Events Reported for at Least 10% of Subjects (Safety Population) in Study VEG105192

Preferred Term	Number (% of subjects)					
	Placebo (n=145)			Pazopanib (n=290)		
	Any Grade	Grade 3	Grade 4	Any Grade	Grade 3	Grade 4
Any AEa	107 (74)	21 (14)	8 (6)	268 (92)	96 (33)	20 (7)
Diarrhea	13 (9)	1 (<1)	0	150 (52)	9 (3)	2 (<1)
Hypertension	15 (10)	1 (<1)	0	115 (40)	13 (4)	0
Hair color changes	4 (3)	0	0	109 (38)	1 (<1)	0
Nausea	13 (9)	0	0	74 (26)	2 (<1)	0
Anorexia	14 (10)	1 (<1)	0	65 (22)	6 (2)	0
Vomiting	11 (8)	3 (2)	0	61 (21)	6 (2)	1 (<1)
Fatigue	11 (8)	2 (1)	2 (1)	55 (19)	7 (2)	0
ALT increased	5 (3)	1 (<1)	0	53 (18)	18 (6)	3 (1)
AST increase	5 (3)	0	0	43 (15)	13 (4)	1 (<1)
Asthenia	12 (8) ^b	0	0	41 (14)	8 (3)	0
Abdominal pain	2 (1)	0	0	32 (11)	6 (2)	0
Headache	7 (5)	0	0	30 (10)	0	0

a. AEs are ranked by incidence in the pazopanib arm. Any AE, any grade includes Grade 5 (fatal) events (12 [4%]

subjects in the pazopanib arm and 4 [3%] subjects in the placebo arm).

b. One placebo subject had Grade 5 asthenia.

ALT= alanine aminotransferase; AST= aspartate aminotransferase

Appendix VIII**Table 78** Adverse reactions by Organ Class and Frequency, Reported in RCC (VEG105192) and STS (VEG110727) Studies

	Frequency classification	
	RCC VEG105192 n=290	STS VEG110727 n=240
Blood and lymphatic system disorders		
Neutropenia	Common	†
Thrombocytopenia	Common	†
Endocrine disorders		
Hypothyroidism*	Common	Common
Metabolic and nutrition disorders		
Anorexia	Very common	Very common
Weight decreased	Common	Very common
Nervous system disorders		
Dizziness	†	Very common
Dysgeusia	Common	Very common
Headache	Very common	Very common
Ischaemic stroke*	Uncommon	Uncommon
Transient ischaemic attack*	Common	†

CONFIDENTIAL

RR2002/00017/11
Oncology

	Frequency classification	
	RCC VEG105192 n=290	STS VEG110727 n=240
Cardiac disorders		
Bradycardia [^]	Very common	Very common
Cardiac dysfunction (such as a decrease in ejection fraction and congestive heart failure)*	Uncommon	Common
Myocardial infarction*	Uncommon	Common
Myocardial ischaemia	Common	♦
QT prolongation*	Common	Common
Torsade de Pointes*	Uncommon	♦
Vascular disorders		
Cerebral haemorrhage*	Uncommon	Uncommon
Epistaxis	Common	Common
Gastrointestinal haemorrhage*	Uncommon	Uncommon
Haematuria	Common	Uncommon
Hypertension*	Very common	Very common
Pulmonary haemorrhage*	Uncommon	Common
Venous thromboembolic events*	Uncommon	Common
Respiratory, thoracic and mediastinal disorders		

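### The automatic accrual-suspension rule in Section 16.42 exempts hypertension, diarrhea and abnormal liver tests at grades 4 and 5, with no cap and no boundary of their own

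*Combined protocol and SAP*

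**What the plan says.** Section 16.42 (Adverse Event Stopping Rules) applies to related events only: "Accrual will be temporarily suspended to this study if at any time we observe events considered at least possibly related to study treatment". The boundary is: "If 4 or more patients in the first 15 treated patients or anytime thereafter more than 25% of patients experience a" grade 4 or higher event, "except for hypertension, diarrhea, and abnormal liver function tests, accrual will be temporarily suspended". No grade limits the exception, and no other boundary is set for the three terms.

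Around the rule, the plan offers softer controls:

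- The team has discretion: "The study team may choose to suspend accrual because of unexpected adverse event profiles that have not crossed the specified rule below".
- The rule itself may be adjusted "at any time during the conduct of the trial and in consideration of newly acquired information regarding the adverse event profile".
- The DSMB "is responsible for reviewing accrual and safety data for this trial at least twice a year" (Section 16.41). The study chair and statistician also review at least twice a year.
- Grade 4 and 5 events judged unrelated or unlikely to be related get an extra attribution check. Related events in the exempt categories fall outside it.

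Background rates are in Appendix VII, Table 14 ("Adverse Events Reported for at Least 10% of Subjects (Safety Population) in Study VEG105192") and in the laboratory tables of Appendix VIII (Tables 79 and 80). The plan gives no operating characteristics for the rule.

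**The concern.** This is the only safety boundary in the plan that requires accrual to pause. As worded, 15 of 15 patients with related grade 4 diarrhea, hypertension or liver test abnormality would add nothing to its count. An exemption makes sense for a term so frequent at the counted grade that it would cause false alarms, but the plan's own tables show these terms to be rare at grade 4.

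The plan treats the same terms more tightly elsewhere. Section 10.31 waives expedited reporting for hypertension and diarrhea only at grade 3, and withdraws the waiver on hospitalization. Section 8.4 defines liver event stopping criteria and 24-hour SAE reporting. Section 16.42 alone has no cap. What is at stake is automatic detection of a cluster of severe events under three known toxicities of the drug.

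**Working it through.** **Inputs from the documents**

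| Quantity | Source | Value |
|---|---|---|
| Early boundary | 16.42 | 4/15 = 26.7%, in line with the later limit of 25% |
| Planned accrual | 16.22 | 35 + 4 = 39 |
| Grade 4 diarrhea, RCC | Table 14 | 2/290 = 0.69% |
| Grade 4 hypertension, RCC | Table 14 | 0/290 = 0% |
| Grade 4 ALT, RCC | Table 14 | 3/290 = 1.03% |
| Grade 4 AST, RCC | Table 14 | 1/290 = 0.34% |
| Grade 4 ALT, RCC laboratory | Table 79 | 2% |
| Grade 4 ALT / AST, STS laboratory | Table 80 | 2% / 3% |
| Any grade 4; grade 5, RCC | Table 14 and footnote | 20/290 = 6.9%; 12/290 = 4.1% |

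The percentages printed in Table 14 reproduce from the counts. If the six exempt-term events fell in six different patients, their combined rate is 6/290 = 2.07%, an upper bound.

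**Step 1: would these terms alone cause false alarms?** The chance of reaching the early boundary is P(X ≥ 4) = 1 − Σ(k=0..3) C(15,k) p^k (1−p)^(15−k). At p = 3% this is 1 − (0.63325 + 0.29378 + 0.06360 + 0.00852) ≈ 0.0008. At 2.07% it is 0.0002, and at 1.03% it is 0.000014. Over all 39 patients the figures are 0.0009, 0.0002 and 0.00001.

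**Step 2: what do they add to other toxicity?** Let q be the related non-exempt grade 4-5 rate and e the exempt rate. The documents do not give q, so a range is assumed:

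- 5% is close to (20 − 6)/290 = 4.8%.
- 7% is Table 14's grade 4 total.
- 11% is (20 + 12)/290, grades 4 and 5 together.

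The 7% and 11% values lean high: they include unrelated events and already contain the exempt terms. Assuming independence, the combined rate is 1 − (1−q)(1−e); for q = 7% and e = 3% it is 1 − 0.93 × 0.97 = 9.8%. The whole rule was evaluated by exact sequential binomial recursion: suspend if X ≥ 4 at any n ≤ 15, or X > 0.25n for n = 16 to 39.

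| Assumed q | Current rule | Counting, e = 1% | e = 2% | e = 3% |
|---|---|---|---|---|
| 5% | 0.6% | 1.2% | 2.0% | 3.1% |
| 7% | 2.1% | 3.2% | 4.7% | 6.5% |
| 11% | 9.6% | 12.2% | 15.3% | 18.7% |

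**Step 3: what does the exemption hide?** Take q = 5% and suppose the true exempt rate were 20% or 30% (illustrative values). The combined rates are 1 − 0.95 × 0.80 = 24% and 1 − 0.95 × 0.70 = 33.5%. A rule that counted these events would suspend with probability 69% or 95%. The current rule stays at 0.6% whatever e is.

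**Step 4: time between reviews.** At 1-2 patients a month (Section 16.23), 6 × 1 = 6 to 6 × 2 = 12 patients could enter between six-monthly DSMB reviews.

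**The case against.** The strongest reply is that the automatic boundary is not the only control. The team may suspend accrual, the rule can be changed, and two reviews look at adverse events at least twice a year. Deaths within 30 days of the last dose, and later deaths at least possibly related, need expedited reporting within 24 hours (Section 10.33). The liver events in Section 8.4(C) and (D) go to the drug supplier as SAEs within 24 hours, and patient-level discontinuation rules exist for severe liver events and refractory hypertension. Setting aside expected class effects that have their own management could also be deliberate.

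Much of this stands. A reader might infer that no number of such events could ever pause the trial, or that a fatal one would go unseen. The documents do not support either reading: the gap is in the mandatory boundary only. But the other controls set no accrual threshold. Discretionary suspension is optional and tied to unexpected profiles. Section 10.2 defines unexpected events as those not listed in Section 15, and Section 15.17 lists hypertension, diarrhea and raised ALT and AST. A note in 10.2 adds severity and frequency, so coverage is arguable. No stated rationale links class-effect management to the exemption.

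Three further limits are fair:

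- Citing only 0-1% background rates would be selective. The laboratory tables reach 2-3%, and Appendix VIII notes that laboratory findings became adverse events at the investigator's discretion.
- The exemption does prevent some pauses. At e = 3% the suspension chance roughly triples at q = 7% and doubles at q = 11%.
- The documents give no grade 5 count for any exempt term, and whether a liver death falls under abnormal liver function tests depends on coding. The frequency of fatal exempt events is unknown.

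**Conclusion.** The point holds for the automatic rule. Related grade 4-5 events under the three terms cannot cross the only mandatory accrual boundary, and the exemption is not needed to control false suspensions from these terms alone (0.00001 to 0.0008 for the early boundary at 1-3%). Counting them costs about 1 to 4 percentage points of suspension probability at a 7% non-exempt rate (from 2.1% to 3.2-6.5%) and about 3 to 9 at 11% (from 9.6% to 12.2-18.7%), the latter overstated because attribution is ignored. In return, the rule regains most of its power to react to a true cluster.

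These figures rest on assumed non-exempt rates, on independence between exempt and non-exempt events, and on background rates from other pazopanib studies. This is an inexpensive improvement to a monitoring rule. It does not show that patients would go unmonitored.

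**What to change.** Amend Section 16.42 so that:

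1. At least possibly related grade 5 events always count, whatever the term.
2. Related grade 4 events under the three terms, at minimum the liver events, either count toward the existing boundary or have a stated boundary of their own.
3. The rule's operating characteristics are given over a range of true rates. The table above serves if the events simply count; a separate boundary needs its own calculation.

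If Section 8.4(D) liver events are used as the liver trigger, say that this is not a grade 4 threshold (it starts at ALT above 3 × ULN with raised bilirubin or hypersensitivity symptoms) and state its expected rate as an assumption. The documents give no rate for it, so its effect on the suspension probability has not been calculated here.

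The cost is one edit and a modestly higher chance of a temporary accrual pause. Patient-level management is unchanged.

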16.6 Inclusion of Women and Minorities

16.61 This study will be available to all eligible patients, regardless of race, gender, or ethnic origin.

- 16.62 There is no information currently available regarding differential effects of this regimen in subsets defined by race, gender, or ethnicity, and there is no reason to expect such differences to exist. Therefore, although the planned analysis will, as always, look for differences in treatment effect based on racial and gender groupings, the sample size is not increased in order to provide additional power for subset analyses.
- 16.63 The geographical region served by Mayo Clinic sites, has a population which includes approximately 10 % minorities. Based on prior Mayo Clinic sites only studies involving similar disease sites, we expect about 10 % of patients will be classified as minorities by race and about 50 % of patients will be women. Expected sizes of racial by gender subsets for patients registered to this study are shown in the following table:

Accrual Targets			
Ethnic Category	Sex/Gender		
	Females	Males	Total
Hispanic or Latino	1	1	2
Not Hispanic or Latino	18	19	37
Ethnic Category: Total of all subjects	19	20	39
Racial Category			
American Indian or Alaskan Native	1	0	1
Asian	0	1	1
Black or African American	1	1	2
Native Hawaiian or other Pacific Islander	0	0	0
White	17	18	35
Racial Category: Total of all subjects	19	20	39

- Ethnic Categories:**
- Hispanic or Latino** – a person of Cuban, Mexican, Puerto Rican, South or Central American, or other Spanish culture or origin, regardless of race. The term “Spanish origin” can also be used in addition to “Hispanic or Latino.”
- Not Hispanic or Latino**
- Racial Categories:**
- American Indian or Alaskan Native** – a person having origins in any of the original peoples of North, Central, or South America, and who maintains tribal affiliations or community attachment.
- Asian** – a person having origins in any of the original peoples of the Far East, Southeast Asia, or the Indian subcontinent including, for example, Cambodia, China, India, Japan, Korea, Malaysia, Pakistan, the Philippine Islands, Thailand, and Vietnam. (Note: Individuals from the Philippine Islands have been recorded as Pacific Islanders in previous data collection strategies.)
- Black or African American** – a person having origins in any of the black racial groups of Africa. Terms such as “Haitian” or “Negro” can be used in addition to “Black or African American.”
- Native Hawaiian or other Pacific Islander** – a person having origins in any of the original peoples of Hawaii, Guam, Samoa, or other Pacific Islands.
- White** – a person having origins in any of the original peoples of Europe, the Middle East, or North Africa.

17.0 Pathology Considerations/Tissue Biospecimens

None

18.0 Records and Data Collection Procedures

18.1 Submission Timetable

Initial Material(s) -

CRF	Active-Monitoring Phase (Compliance with Test Schedule Section 4.0)
On-Study Form ¹	≤ 2 weeks after registration
Adverse Events: Baseline	
RECIST Measurements: Baseline	
Specimen Submission: Blood (see Section 14.0)	
Specimen Submission: Urine (see Section 14.0)	
Laboratory Tests and Results	
Concomitant Medication Form	
Patient Status: Baseline	
Off Treatment ²	Submit ≤ 2 weeks after registration if withdrawal/refusal occurs prior to beginning protocol therapy

1. On-Study: Prior Surgery, On-Study Prior Radiation, and On-Study Prior Systemic Therapy will be added as needed.
2. Added if needed based on the responses on the Patient Status: Baseline form

Central Pathology Review Material(s) -

CRF	Active-Monitoring Phase (Compliance with Test Schedule Section 4.0)
Pathology Materials (this is for central review, eligibility, etc.)	Submit ≤30 days after registration

Test Schedule Material(s) -

CRF	Active-Monitoring Phase (Compliance with Test Schedule Section 4.0)	
	At each evaluation during treatment	At end of treatment
Treatment (Intervention)	X ¹	X
Adverse Events: Solicited	X	X
RECIST Measurement ² s	X	X
Specimen Submission: Blood	X (see Section 14.0)	
Specimen Submission: Urine	X (see Section 14.0)	
Laboratory Tests and Results	X	X
Concomitant Medications	X	X
Patient Status: Treatment	X	
Off Treatment ²		X
Notification Form – Grade 4 or 5 Non-AER Reportable Events/Hospitalization Form	At each occurrence (see Section 10.0)	
ADR/AER	At each occurrence (see Section 10.0)	

1. Complete at each evaluation during Active Treatment (see Section 4.0).
2. Added if needed based on the responses on the Patient Status: Treatment form

Follow-up Material(s) -

CRF	Survival Follow-up Phase¹				
	q.  3  months until PD	At PD ¹	After PD q.  6  mos.	Death	New Primary
Patient Status: Survival Follow-up ¹	X ²	X ²	X	X	At each occurrence

1. If a patient is still alive 2 years after registration, no further follow-up is required.
2. Submit copy of documentation of response or progression to the MCCC Operations Office, Attention: QAS for MC1152

- 18.2 Patient identification labels will be produced for each patient entry. The labels are produced for use on the data forms and will be mailed to the co-sponsors/participants twice. Additional labels may be obtained by directly calling the Mayo Clinic Cancer Center (MCCC) Registration Office [REDACTED].
- 18.3 Each co-sponsor/participant will be responsible for insuring that all materials contain the patient's initials, MCCC registration number, and MCCC protocol number. Patient's name must be removed.
- 18.4 Any materials deemed incomplete by the MCCC Operations Office will be considered "not received" and will not be edited or otherwise processed until the missing information is received. A list of the missing documents will be made available to the appropriate co-sponsor/participant.
- 18.5 Overdue lists: A list of overdue materials and forms for study patients will be generated monthly. The listings will be sorted by location and will include the patient study registration number. The appropriate co-sponsor/participant will be responsible to obtain the overdue material.
- 18.6 Corrections forms: If a correction is necessary the QAS will query the co-sponsor/participant. The query will be sent to the appropriate co-sponsor/participant who will make the correction and return the query and documentation of correction back to the QAS.

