16.0 Statistical Considerations and Methodology

- 16.1 Overview: This protocol will assess the efficacy of pazopanib in patients with non-clear cell metastatic renal cancer using a one-stage phase II study design.
- 16.11 Primary Endpoint: The primary endpoint of this trial is the 12-month overall survival rate. A “12-month overall survivor” will be considered synonymous with “success”, unless otherwise specified. A patient is considered to be a 12-month survivor if the patient lives 12 months from registration (note, all deaths prior to 12 months, regardless of cause, will be considered a failure). All patients meeting the eligibility criteria who have signed a consent form and have begun treatment will be evaluable for the primary endpoint. All eligible patients will be followed until death or a minimum of 2 years.
- 16.2 Statistical Design:
- 16.21 Decision Rule: The largest success proportion where the proposed treatment regimen would be considered ineffective in this population is 55%, and the smallest success proportion that would warrant subsequent studies with the proposed regimen in this patient population is 75%. The one-stage design based on properties of the binomial distribution uses 39 patients to test the null hypothesis that the true success proportion in a given patient population is at most 55%.
- 16.22 Sample Size: There will be 35 evaluable patients accrued onto this study unless undue toxicity is encountered. We anticipate accruing an additional 4 patients to account for ineligibility, cancellation, major treatment violation, or other reasons.
- 16.23 Accrual Time and Study Duration: The anticipated accrual rate is approximately 1-2 patients per month, based on the incidence of tumor type and the potential to accrue at Mayo Clinic sites (Mayo Clinic Rochester, Mayo Clinic Florida and Mayo Clinic Arizona). Therefore, the accrual period for this phase II study is expected to be 24 months. The final analysis can begin approximately 36 months after the trial begins, i.e. as soon as the last patient has been observed for 12 months.

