- 16.24 Power and Significance Level: The null 12-month overall survival rate of 55% is based on the Kaplan-Meier estimate of 12-month survival from the Mayo Clinic Nephrectomy database (Leibovich, Lohse et al.). Assuming that the number of successes is binomially distributed and the significance level is ≤ 0.10 , we are required to accrue evaluable 35 patients to achieve an 80% power under the alternative hypothesis of a 75% success proportion.
- 16.3 Analysis Plan: The analysis for this trial will commence at the time all patients have become evaluable for the primary endpoint. Such a decision will be made by the Statistician and Study Chair, in accord with standard operating procedures, availability of data for secondary endpoints, and the level of data maturity.

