16.31 Primary Endpoint

- 16.311 The primary endpoint of this trial is the 12-month overall survival rate. This endpoint has been described as a binomial endpoint of success and failure, therefore patients lost to follow-up (eg, progressed/recurred, refusing further study participation, etc) prior to the time necessary for the binomial endpoint (eg, 12 months) will be defined as failure. All patients meeting the eligibility criteria who have signed a consent form and have begun treatment will be considered evaluable for the primary endpoint. All eligible patients will be followed until death or a minimum of 2 years.
- 16.312 Estimation: The proportion of successes will be estimated by the number of successes divided by the total number of evaluable patients. Confidence intervals for the true success proportion will be calculated.
- 16.313 Over Accrual: If more than the target number of patients are accrued, the additional patients will not be used to evaluate the stopping rule or used in any decision making processes; however, they will be included in final point estimates and confidence intervals.

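### No survival contact is tied to month 12 after progression, so some 12-month outcomes may be unrecorded at the earliest analysis date and Section 16.311 could score them as failures: a cheap improvement

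*Combined protocol and SAP*

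**What the plan says.** **Endpoint.** Section 16.11 counts a patient as a success if he or she lives 12 months from registration.

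**Contacts.** While on treatment, patients are seen at least every 28 days (Section 7.3). Progression ends treatment (7.4) and moves the patient to event monitoring (13.2). The follow-up table in Section 18.1 then asks for a survival form every 3 months until progression, at progression, every 6 months after progression, and at death. The after-progression column does not say whether its interval runs from progression or from registration. The footnote reads "If a patient is still alive 2 years after registration, no further follow-up is required".

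**Analysis time.** Section 16.23 expects 24 months of accrual and lets the final analysis begin at about month 36, "as soon as the last patient has been observed for 12 months". Section 16.3 starts it when all patients are evaluable for the primary endpoint, and leaves the decision to the statistician and study chair in view of data maturity, among other things. Section 16.5 places primary completion when the last registered patient has been followed for 12-month survival status.

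**Missing status.** Under Section 16.311, patients lost to follow-up "prior to the time necessary for the binomial endpoint (eg, 12 months) will be defined as failure". Progression or recurrence is listed there as an example of such loss. Sections 16.11 and 16.311 define evaluable as eligible, consented and having begun treatment.

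**The concern.** The patients with the sparsest contact are those who have progressed, and no scheduled form establishes whether they were alive at month 12. If the interval runs from progression, a patient who progresses at month 4 has forms at months 10 and 16 and none between.

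The trigger in 16.3 does not close this gap by itself. A patient becomes evaluable on starting treatment, long before 12-month status can be known. Section 16.311 then supplies a rule that could turn the gap into failures, and its example names the group concerned. That example also conflicts with 16.11, under which a progressed patient who lives 12 months is a success.

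At stake are a 12-month survival rate estimated too low and a loss of power in a test with 35 evaluable patients.

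**Working it through.** **1. The plan's own design.** The inputs come from Sections 16.21 and 16.24.
- Null: "The largest success proportion where the proposed treatment regimen would be considered ineffective in this population is 55" per cent.
- Alternative: "the smallest success proportion that would warrant subsequent studies with the proposed regimen in this patient population is 75" per cent.
- Level: "the significance level is ≤ 0.10". It is read as one-sided, because the null is that the success proportion is at most 55%.
- Size: "we are required to accrue evaluable 35 patients to achieve an 80% power". Section 16.21 gives 39 as the number tested, while 16.22 and 16.24 give 35 evaluable; 35 is used here.

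No cut-off is printed. With X binomial on 35 patients:
- P(X ≥ 23 | 0.55) = 0.134, above 0.10.
- P(X ≥ 24 | 0.55) = 0.073, so 24 is the smallest admissible cut-off.
- P(X ≥ 24 | 0.75) = 0.858.

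So 35 patients meet both stated limits.

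**2. Length of the gap.** Assume contacts run from progression, at month t < 12. The first contact at or after month 12 then falls at 12 + (t mod 6).

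| Progression at month | First contact at or after month 12 | Delay (months) |
|---|---|---|
| 1 or 7 | 13 | 1 |
| 3 or 9 | 15 | 3 |
| 5 or 11 | 17 | 5 |
| 6 | 12 | 0 |

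The delay is always under 6 months. If contacts run from registration, one falls at month 12 and there is no delay. At month 36, therefore, only patients registered in the last 6 months of accrual can be pending: 6/24 = 25% under uniform accrual.

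**3. How many could be pending.** Assumptions not in the documents: uniform accrual over 24 months, contacts counted from progression, exponential progression-free survival with median m (rate λ = ln 2 / m), and deaths ignored. For an analysis d months after month 36:

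share pending = (1/24) × e^(−dλ) × (1/λ) × [1 − e^(−(6−d)λ)(1 + (6−d)λ)] × (1 + e^(−6λ))

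For m = 3 and d = 0, λ = 0.231 and the mean delay is 4.328 × (1 − 0.25 × 2.386) × 1.25 = 2.18 months. The share is 2.18/24 = 9.1%, or 3.2 of 35.

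| Median PFS (months) | Pending at month 36 | Of 35 | Of 35 at month 38 | Of 35 at month 42 |
|---|---|---|---|---|
| 3 | 9.1% | 3.2 | 1.2 | 0 |
| 6 | 8.3% | 2.9 | 1.2 | 0 |
| 9 | 7.0% | 2.4 | 1.0 | 0 |

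**4. Effect if every pending patient is scored as a failure.** Forcing k patients to failure, whatever their true status, leaves 35 − k who can succeed:
- k = 2: P(X ≥ 24 | 33, 0.75) = 0.701; alpha P(X ≥ 24 | 33, 0.55) = 0.029.
- k = 3: P(X ≥ 24 | 32, 0.75) = 0.594; alpha P(X ≥ 24 | 32, 0.55) = 0.016.

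If the k patients are all truly alive at month 12, the test needs 24 + k true survivors. Then P(X ≥ 26 | 35, 0.75) = 0.626 and P(X ≥ 27 | 35, 0.75) = 0.474.

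The number pending is random. Averaging over it, with survival independent of progression, means using success probability 0.75 × (1 − share). Power is then 0.56 to 0.64 across the three medians. In every variant alpha is below 0.073.

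**The case against.** A reader might infer that the schedule builds in unknown outcomes and that the plan then counts living patients as dead. The documents do not support that, for these reasons.

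- **Pending is not lost.** The 16.311 rule is written for patients lost to follow-up. A patient whose next form is due at month 13 to 17 is still being followed, and follow-up runs to death or 2 years. A later contact or a death form settles 12-month status. This largely stands. What remains is that 16.311 itself offers progression as an example of loss, so scoring such a patient as a failure is a possible reading but not a stated instruction.
- **The analysis may wait.** Section 16.23 says when the analysis can begin, not when it must. A patient last contacted at month 10 has arguably not been observed for 12 months. Data maturity (16.3) and the completion definition (16.5) point the same way. This stands as permission to wait, but nothing requires a dated status for each patient.
- **The starting point is not printed.** Counting from progression is the natural reading of the column, but counting from registration would remove the gap. This stands, and the ambiguity is itself worth a line.
- **A form timetable is a minimum.** Nothing in 18.1 bars a status query before data lock. That is true, but none is written.

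The 2-year footnote is not evidence of the gap, since it shows follow-up continuing a year past the endpoint. The evidence is the after-progression column of the same table.

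**Conclusion.** The point holds as a cheap improvement. No contact is tied to month 12 after progression, and the analysis trigger does not guarantee a known 12-month status. The loss-to-follow-up example in 16.311 contradicts the endpoint definition in 16.11.

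The size depends on a chain of conditions: contacts counted from progression, analysis at exactly month 36, no status query beforehand, and every pending patient scored as a failure. With the accrual and progression assumptions above, about 2.4 to 3.2 of 35 patients are pending. Power drops from 0.86 to 0.70 (2 forced to failure) or 0.59 (3 forced to failure), and further if all of them are truly alive. If any one of these conditions fails, the loss shrinks or disappears. Waiting alone brings the count to about 1 by month 38 and zero by month 42.

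Any bias is towards failure. It lowers the estimated rate and the power, and it does not raise the type I error. The conflict between 16.11 and 16.311 needs none of these assumptions.

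**What to change.** 1. **Section 18.1:** add one vital-status check, by phone or record, at 12 to 13 months from registration for every patient, whatever the progression status. State whether the 6-month interval runs from progression or from registration.
2. **Sections 16.23 and 16.3:** start the primary analysis only when each patient has a death date, a contact dated at or after 12 months, or documented true loss to follow-up.
3. **Section 16.311:** remove progression and recurrence as examples of loss, and state that neither progression nor a pending contact is loss to follow-up. The month-12 check alone would leave this conflict in place.

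The cost is about 39 calls or chart checks (35 evaluable plus 4 additional patients) and possibly a few weeks' delay to the analysis. The sample size does not change: with status known for everyone, 35 patients and a cut-off of 24 give alpha 0.073 and power 0.858.
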